13.1.2.3 Secondary Efficacy Variables

- Percentage of subjects on continuous BRV monotherapy for at least 3 months, at least 6 months, and at least 12 months of the Evaluation Period

13.1.2.4 Other Efficacy Variables

- Partial onset seizure (type I) frequency per 28 days during the Evaluation Period

- Percent reduction in POS (type I) frequency per 28 days from Baseline of the previous study to the Evaluation Period
- Percentage of subjects continuously seizure-free for all seizure types (I+II+III) for at least 6 months and at least 12 months during the Evaluation Period
- Change in QOLIE-31-P scores from Baseline of the previous study to each assessment for the first 2 years and to the last Evaluation Period assessment during the first 2 years
- EuroQoL-5 Dimensions questionnaire response for each assessment for the first 2 years for the Evaluation Period and for the last assessment during the first 2 years of the Evaluation Period

13.1.2.5 Pharmacoeconomic Variables

- Direct costs (healthcare provider consultations not foreseen by the protocol, concurrent medical procedures, concomitant medications, hospitalizations, and ER visits) during the first 2 years of the Evaluation Period
- Indirect costs (workdays or schooldays lost by the subject and days subject received help from a caregiver) during the first 2 years of the Evaluation Period
- Socio-professional data for each assessment for the first 2 years and for the last assessment during the first 2 years of the Evaluation Period

13.1.2.6 Pharmacokinetic Variables

- Brivaracetam (parent compound only) plasma levels
- Concomitant AED (and/or relevant metabolites) plasma levels

13.1.3 Statistical Evaluation

Descriptive statistics, such as the mean, standard deviation, median, 25th percentile, 75th percentile, minimum value, and maximum value for quantitative variables, and counts and percentages for categorical variables, will be provided. Key supporting data will be provided in data listings. Summary statistics will be presented by the overall BRV dose.

For the purpose of statistical analysis, the following periods are considered:

- Evaluation Period (V1 until the last Evaluation Visit)
- Down-Titration Period
- Post-Treatment Period

13.1.3.1 Evaluation of Safety

All safety variables will be analyzed by descriptive methods on the Safety Population. Treatment-emergent adverse events will be summarized by categories of total duration of exposure, period, Medical Dictionary for Regulatory Activities (MedDRA[®]) Primary System

Organ Class and Preferred Term in incidence tables. Separate tables will be provided, by categories of total duration of exposure, for AEs leading to withdrawal from the study and SAEs.

Changes in laboratory values, vital signs, and weight will be summarized by visit. Possibly clinically significant treatment-emergent abnormalities for laboratory values, vital signs, and weight will be listed and summarized by analysis period. Electrocardiogram abnormalities, as well as physical and neurological abnormalities, will be presented in subject data listings.

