13.4.2 Handling of Dropouts of Missing Data

Safety and efficacy variables will be analyzed insofar as they are available. Days with missing information will be ignored in the calculation of the seizure frequency per week.

Since subjects will drop out at different times from the study, the results will be presented by categories of duration of exposure where applicable.

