### 2.2 Study Variables

#### 2.2.1 Safety variables

##### 2.2.1.1 Primary safety variables

- Occurrence of a treatment-emergent adverse event (TEAE)
- Withdrawal due to adverse event (AE)
- Occurrence of a serious adverse event (SAE)

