## 11.1 Extent of Exposure

### 11.1.1 Number of subjects exposed and subject-years of exposure

A daily dose will be calculated for each study day from the day of first dose of BRV to the day of last dose of BRV for the purposes of calculating modal dose. Daily dose will be calculated as the sum of the AM and PM dose for each day.

Modal daily doses will be calculated across all study days on or after the day of first dose of BRV and up to and including the day of last dose of BRV. Modal daily dose is the most frequently taken daily dose during this period. In the event of a tie, the modal dose will be set to the lower of the tied doses. Modal daily dose will be categorized as follows:

| Category  | Definition               |
|-----------|--------------------------|
| 5 mg/day  | <20mg/day                |
| 20mg/day  | ≥20mg/day to <50mg/day   |
| 50mg/day  | ≥50mg/day to <100mg/day  |
| 100mg/day | ≥100mg/day to <150mg/day |
| 150mg/day | ≥150mg/day to <200mg/day |
| 200mg/day | ≥200mg/day               |

Subject years of exposure will be calculated by summing the exposure duration in days for all subjects being summarized, and dividing the resulting value by 365.25.

Subject years of exposure will be presented overall and by modal dose for the Safety Analysis Set. The subject years of exposure presented by modal dose will be the total subject years of exposure of subjects with that modal dose.

The number and percentage of subjects exposed to BRV will be summarized overall and by modal dose category. The number and percentage of subjects in each Exposure Duration Cohort (≥3 months, ≥6 months, ≥12 months, and so forth) will be summarized.

The number and percentage of subjects within each modal dose category will be summarized for each Exposure Duration Cohorts; percentages will be relative to the total number of subjects in each Exposure Duration Cohort.

In addition to the overall summaries of the above, the above will also be summarized by subgroup for region.

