#### *Serious Adverse Events*

- Incidence of treatment-emergent SAEs

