### *Discontinuations due to TEAE*

- Incidence of TEAEs leading to permanent discontinuation of study drug

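### The SAP omits, without declaring it, the exposure-duration tables that the protocol promises for SAEs and for AEs leading to withdrawal

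*Protocol*

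**What the plan says.** Protocol 13.1.3.1 plans TEAE tables by exposure-duration category and then makes a specific commitment on two further outcomes: "Separate tables will be provided, by categories of total duration of exposure, for AEs leading to withdrawal from the study and SAEs". Protocol 13.4.2 gives the general reason: "Since subjects will drop out at different times from the study, the results will be presented by categories of duration of exposure where applicable".

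SAP 2.2.1.1 names both outcomes as primary safety variables, next to the occurrence of any TEAE. For SAEs, SAP 11.2.2 lists a single item, "Incidence of treatment-emergent SAEs". For withdrawals it lists "Incidence of TEAEs leading to permanent discontinuation of study drug". Unless otherwise stated, the tables in that section are by MedDRA system organ class and preferred term and pool the Evaluation, Down-Titration and Post-Treatment Periods. Both outcomes also have a line in the overall AE summary, which is repeated by geographic region.

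Tables by 3-month interval are listed for all TEAEs, for TEAEs in at least 5% of subjects and for TEAEs of interest. SAP 3.2.7 defines exposure duration cohorts (all subjects, then at least 90, 180 and 360 days, then 6-month steps). On person-time, SAP 11.1.1 says: "Subject years of exposure will be presented overall and by modal dose for the Safety Analysis Set".

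**The concern.** The primary objective is long-term safety and tolerability. Exposure differs widely between subjects: the lowest cohort in SAP 3.2.7 starts at 1 day, and the Kaplan-Meier retention estimates in SAP 5.1 run to 60 months. A percentage over all treated subjects then depends on two things, how often the event occurs and how long people stay on drug. It cannot show whether SAEs or AE-related discontinuations fall early or keep accruing, which is what a long-term follow-up study is best placed to show. The protocol foresaw staggered dropout and promised tables to deal with it. The SAP does not carry that promise through for two of its three primary safety variables.

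**Working it through.** The plan has no sample size, alpha or power figure to reproduce. The check compares the two documents and adds an illustration.

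**1. Tables promised and tables listed**

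| Primary safety variable | Protocol 13.1.3.1 | SAP 11.2.2 |
|---|---|---|
| Any TEAE | By exposure category and by period | Overall, by 3-month interval, by study period |
| SAE | Separate table by exposure category | One table, periods pooled |
| Withdrawal due to AE | Separate table by exposure category | One table, periods pooled (permanent discontinuation of study drug) |

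The exposure-category split is lost in all three rows. Only the first row has a substitute with a time dimension. There is also a small change of definition in the last row: the protocol refers to leaving the study, the SAP to stopping the drug.

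**2. Where the SAP uses its exposure variables.** The 3.2.7 cohorts are used for seizure frequency (8.2.1), percent reduction (8.2.2), seizure freedom (8.2.3) and the exposure tables (11.1.1). No AE table uses them. Subject-years appear only in 11.1.1, and no AE rate is built on them.

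**3. Whether the change is declared.** SAP 2.5 lists one departure, the monotherapy analysis. SAP section 14 covers interim-cutoff rules, cost and socio-professional summaries, and the signature page. Neither mentions these tables.

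**4. Illustration of size.** The documents give no SAE or dropout rates, so all rates here are assumptions. Let h be a constant hazard of first SAE, d a constant and independent dropout hazard, and T = 5 years the cap.

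Whole-study percentage = h/(h+d) × (1 − exp(−(h+d)T))

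With h = 0.08 per year:
- d = 0.10: 0.08/0.18 × (1 − exp(−0.90)) = 0.264
- d = 0.25: 0.08/0.33 × (1 − exp(−1.65)) = 0.196
- d = 0.50: 0.08/0.58 × (1 − exp(−2.90)) = 0.130

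The risk at a fixed exposure t is 1 − exp(−0.08t): 2.0% at 3 months, 7.7% at 1 year and 33.0% at 5 years, whatever the dropout.

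The range over other assumed values, with T = 5, is:

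| h per year | 12-month risk | d = 0.2 | d = 0.5 | d = 1.0 |
|---|---|---|---|---|
| 0.05 | 4.9% | 14.3% | 8.5% | 4.7% |
| 0.10 | 9.5% | 25.9% | 15.8% | 9.1% |
| 0.20 | 18.1% | 43.2% | 27.7% | 16.6% |

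The last three columns are whole-study percentages. In each row the event hazard is fixed and only retention changes.

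**5. Which split shows timing.** The 3.2.7 cohorts are nested and defined by total exposure reached. A subject who stops for an AE on day 60 belongs to the all-subjects cohort and to no other. The cohort with at least 360 days therefore contains nobody who stopped before day 360. For discontinuations, each cohort is conditioned on the event not having happened before its threshold. The interval rule in SAP 3.2.5 works differently: a subject counts in an interval if the last dose falls on or after its first day. The day-60 subject is then counted, with the event, in Months 1-3. The interval tables answer the timing question, and the cohort tables do not.

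**The case against.** A reader might infer that these two variables are reported only as one bare percentage each. That goes too far. The tables are by system organ class and preferred term, the overall summary is repeated by region, adverse event is a separate reason in the disposition summary (SAP 5.1), and subject listings are planned. SAEs also sit inside the all-TEAE interval tables, though not shown separately. What stands is that every tabulation specific to these two variables covers the whole study, with no time or exposure split.

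The sponsor could point to SAP 3.2.5, which says that 3-month intervals will be used for AEs. That sentence is general. The list in 11.2.2 names the interval split where it is wanted and leaves it out for these two items. The Kaplan-Meier analysis in SAP 5.1 covers discontinuation for any reason, not AE withdrawal.

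The protocol does leave room. It defers detail to the SAP, qualifies the general rule in 13.4.2, and allows changes to be discussed in the study report (13.3). This softens the non-disclosure, but 13.1.3.1 names the two tables without qualification.

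A reader might also infer that the plan should have used rates per subject-year. Neither document promises them. A single rate assumes a constant hazard and so would not show early clustering either, and an approximate SAE rate can already be formed from the planned SAE count and total subject-years.

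Finally, this is a descriptive single-arm study and only one dropout pattern will occur. The illustration shows that the percentage is hard to interpret. It does not show bias in a planned comparison.

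**Conclusion.** The point holds as an undeclared departure from the protocol. Two named tables for two of the three primary safety variables are absent from SAP 11.2.2, nothing with a time dimension replaces them, and SAP 2.5 is silent. This conclusion rests on the documents alone.

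The size is illustrative. With an assumed SAE hazard of 0.08 per year over 5 years, the whole-study percentage is 26%, 20% or 13% at dropout hazards of 0.10, 0.25 or 0.50 per year. The direction does not depend on those values: at a fixed hazard and cap, more dropout lowers the percentage. The calculation covers SAEs only and assumes constant, independent hazards. AE withdrawal, which itself ends exposure, is not quantified.

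**What to change.** In SAP 11.2.2, add treatment-emergent SAEs and TEAEs leading to permanent discontinuation by 3-month interval, with the AE inclusion rule already in SAP 3.2.5. Under 11.2.2 the interval tables take only events with onset up to the last dose, so keep the pooled tables for post-treatment events.

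Then do one of two things about the exposure-category tables:
- Restore them for both variables. The protocol does not define its categories, so the SAP should say which it uses. If these are the 3.2.7 cohorts, a footnote should say that subjects who discontinued before each threshold are left out.
- Declare and justify in SAP 2.5 that the interval tables replace them.

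Either way, 2.5 should record that interval tables replace the exposure-category split for TEAEs as a whole. It should also note the difference between leaving the study and stopping the drug. Rates per subject-year are an optional supplement.

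The cost is some SAP wording and a few tables from variables already derived, with no new data. Later intervals will be sparse. Of the 108 subjects enrolled, 108 × exp(−d) gives about 88, 66 or 40 still on drug at 12 months for assumed dropout hazards of 0.2, 0.5 or 1.0 per year, and 108 × exp(−5d) gives about 40, 9 or 1 at 60 months. Each interval should show its denominator.

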13.1.3.2 Evaluation of Efficacy

13.1.3.2.1 Efficacy Analyses

All efficacy analyses will be based on the Efficacy Population. All efficacy variables will be analyzed descriptively. The Baseline of an efficacy variable will be the Baseline from the previous study.

The secondary efficacy variables for the cumulative proportion of subjects remaining on BRV monotherapy from the start of the study through 3, 6, and 12 months will be estimated using Kaplan-Meier methods.

13.1.3.2.2 Other Efficacy Analyses

The percentage reduction in 28-day POS frequency relative to Baseline will be summarized using descriptive statistics. Baseline will be defined as the Baseline value from the previous study. Additionally, the number and percentage of subjects continuously seizure-free during the Evaluation Period will be presented. Descriptive statistics for the change in QOLIE-31-P and EQ-5D from Baseline of the previous study to each visit during the first 2 years of the study and the last Evaluation Period Visit will also be presented.

13.2 Determination of the Sample Size

For this open-label, LTFU study, no sample size calculation has been performed. The sample size will depend upon recruitment into and completion of preceding studies; approximately 300 - 600 subjects were expected.

13.3 Changes in the Conduct of the Study or the Planned Analyses

An SAP will be developed and approved prior to the database lock. The full details of the statistical analyses will be provided in the SAP. Any deviations from the SAP as well as changes from the protocol will be discussed in the Clinical Study Report.

13.4 Statistical and Analytical Issues

13.4.1 Adjustments for Covariates and Interactions

No adjustment for covariates is foreseen.

13.4.2 Handling of Dropouts of Missing Data

Safety and efficacy variables will be analyzed insofar as they are available. Days with missing information will be ignored in the calculation of the seizure frequency per week.

Since subjects will drop out at different times from the study, the results will be presented by categories of duration of exposure where applicable.

13.4.3 Interim Analysis

Due to the single-arm open-label nature of this study, no interim analysis as such will be performed. However, interim database locks will have to be performed to allow safety and efficacy analyses in support of submission activities or to allow optimization of the development program. In addition, an ongoing medical review (Safety Data Review, SDR) applying to the entire BRV program is organized.

13.4.4 Multi-center Studies

No analysis by center is planned.

13.4.5 Multiple Treatment Comparisons/Multiple Endpoints

Not applicable.

13.4.6 Examination of Subgroups

No inferential analyses are planned. Only descriptive summaries will be made on sub-groups of subjects with similar exposure.

13.5 Pre-Analysis Review of Data

A pre-analysis review will take place:

- before starting analysis.
- after all the data have been verified / coded / entered into the database.

The review will be performed to decide how to deal with problems in subject's data (missing values, withdrawals, protocol deviation).

After the pre-analysis review and documentation of all decisions concerning the subjects with problems, the database will be locked.

The analysis will start after the approval and locking of the database, and approval of the final SAP.

13.6 Criteria for Un-blinding the Results

Not applicable

13.7 Dictionaries

Adverse events and concomitant procedures will be coded according to MedDRA dictionary (latest available version).

Medications will be coded according to World Health Organization Drug dictionary (latest available version).

REDACTED COPY
This document cannot be used to support any marketing authorization application and any extensions or variations thereof.

14. ETHICS AND REGULATORY REQUIREMENTS

14.1 Approval

The final protocol and any amendments must be signed by the Principal Investigator of the site and by appropriate representative(s) of UCB.

The final protocol must be submitted to and approved by:

- a duly constituted Independent Ethics Committee (IEC) or Institutional Review Board (IRB).
- the relevant Regulatory Authorities, according to local regulations.

If any alterations to the protocol are required by these bodies, they can be implemented only with the written agreement of the Investigator and the Sponsor's approver(s) before further submission to the requesting body.

A copy of the IEC/IRB's written approval with clear identification of the submitted document(s) and a list of members attending the meeting (listed by function and affiliation) should be forwarded by the Investigator to the Clinical Trial Manager (CTM).

The usual composition of the IRB/IEC (or DHHS number) along with an IRB/IEC Statement of Compliance should also be forwarded to the CTM.

Before submission to an IRB/IEC, the consent form and any other written information to be provided to subjects (e.g., advertisement) must be submitted for internal Sponsor approval. The study is not allowed to start until the protocol and related documents (informed consent, advertisement, etc.) have received written approval from the IEC/IRB and Regulatory Authorities, if applicable, as well as until other GCP prerequisites are fulfilled.

If new information becomes available, it should be communicated without delay to the subject, the Investigator, the IEC/IRB, and regulatory authorities, wherever required.

The IEC/IRB must be notified promptly by the Investigator (or Sponsor, if applicable) in writing of the following:

- Deviations from, or changes to the protocol to eliminate immediate hazards to all the study subjects.
- Significant changes to the conduct of the study. Significant changes to the protocol can only be affected by a formal protocol amendment that must be submitted to the IEC/IRB and approved prior to implementation at the site.
- New information that may adversely affect subject safety or the conduct of the study.

The Investigator (or Sponsor, if applicable) should comply with the applicable regulatory requirements related to the reporting of safety information to the IEC/IRB and Regulatory Authorities.

14.2 Subject Information and Consent

Adequate information will be provided to the subject in both oral and written form and consent will be obtained in writing prior to performance of any study specific procedure. Where required, the consent form or a specific Assent Form will be signed and dated by minors. The content and process of obtaining informed consent will be in accordance with all applicable regulatory and IEC/IRB requirements.

UCB may provide a sample informed consent form and a subject information sheet. The final consent form must be approved by the IEC/IRB and should contain the applicable ICH-GCP elements in a language readily understood by the subject (i.e., lay terminology) and/or subject's legally representative(s).

If the informed consent form is amended during the study, the Investigator (or the Sponsor, if applicable) must follow all applicable regulatory requirements pertaining to the approval of the amended informed consent form by the IEC/IRB and use of the amended form.

For ■ centers, a separate Health Insurance Portability and Accountability Act (HIPAA) agreement may be used if required by the IRB or institution.

Subjects and/or subjects' legally acceptable representatives will be informed of the purpose of the study in unambiguous language they easily understand. Their participation is voluntary and they can at any time decide to stop their participation without any influence on their future care or treatment. The subjects and/or subject's legally acceptable representatives must be informed about the main procedures used to guarantee their anonymity, especially during the analysis of their personal data. Subjects and/or subjects' legally acceptable representatives should be able to ask any questions about the study and to receive relevant answers. They will receive complete written information in the Subject Information Sheet or Informed Consent Form.

After having received extensive information about the purpose and risks of the study and having had enough time to consider participation in the study, the subject and/or subject's legally acceptable representative(s) must give their written consent by signing and dating the Informed Consent Form. This form will also be signed and dated by the person who obtained the informed consent and then retained by the Investigator. Obtaining of consent will be confirmed in the subject's medical records. The subject and/or subject's legally acceptable representative(s) will receive a copy of the signed and dated consent form and the original will be filed in the Investigator's Study File.

If the signature of a witness is required, the witness should sign and personally date the consent form after the subject and/or subject's legally acceptable representative(s) has signed. By signing the consent form, the witness attests that the information in the consent form and in any other written information was accurately explained to, and apparently understood by, the subject and/or subject's legally acceptable representative(s) and that informed consent was freely given.

The subject and/or subject's legally acceptable representative(s) may withdraw their consent to participate in the study at any time. A subject is considered as enrolled in the study when he/she and/or his/her legally acceptable representative(s) have signed the informed consent form. A Case Report Form must not be started, nor may any study specific procedure be performed for a given subject, without having obtained his/her and/or his/her legally acceptable representative(s) written consent to participate in the study.

If any new information that could influence the subject and/or subject's legally acceptable representative(s) decision to stay in the study becomes available, this information will be transmitted to the subject and/or subject's legally acceptable representative(s) without delay. In addition, the informed consent form must be amended accordingly or a separate consent form be created and submitted to the IEC/IRB for approval prior to being implemented for re-consent of all ongoing subjects and/or subjects' legally acceptable representative(s) in the study and for use in consenting all subjects entering the study from that point forward.

